10.4 Definitions of adverse events of special interest

An adverse event of special interest (AESI) is an AE (serious or non-serious) of scientific and medical concern for which ongoing monitoring and immediate notification to Sanofi PV is required. Such events may require further investigation in order to characterize and understand them. Adverse events of special interest may be added or removed during a study by protocol amendment.

AESI	Definition	
Increase in ALT	ALT >3 x ULN	
Allergic events	Allergic drug reactions and/or local injection site reactions deemed to be	
	allergic by the Investigator (or have an allergic component), that require	
	consultation with another physician for further evaluation of	
	hypersensitivity/allergy as per the Investigator's medical judgment should	
	be reported as an AESI.	
Pregnancy	Pregnancy occurring in a female patient during the study or within	
	70 days following the last dose of study drug.	
	- Pregnancy will be recorded as AESI in all cases. Pregnancy will be	
	qualified as an SAE only if it fulfils one or more SAE criteria.	
	- In the event of pregnancy of a female patient included in the study, study	
	product should be discontinued.	
	- The follow-up of the pregnancy will be mandatory until the outcome has	
	been determined.	
Symptomatic	An overdose (accidental or intentional) is an event suspected by the	
overdose	Investigator or spontaneously notified by the patient (not based on	
	systematic injection counts) and defined as at least twice of the intended	
	dose within the intended therapeutic interval (i.e., 2 or more injections are	
	administered in <7 calendar days), to be reported using the Term	
	"symptomatic OVERDOSE (accidental or intentional), indicating the	
	circumstance in parentheses (e.g., "symptomatic overdose [accidental]" or	
	"symptomatic overdose [intentional]"). The patient should be monitored	
	and appropriate symptomatic treatment instituted.	
	- The circumstances of the overdose should be clearly specified in the	
	verbatim and symptoms, if any, entered on separate AE/SAE forms.	
	- Of note, asymptomatic overdose should be reported as a standard AE.	

Adverse events of special interest (AESI) in this study include the following:

Neurologic events	Neurologic events that require additional examinations/procedures and/or	
	referral to a specialist should be reported as an AESI. If the event does not	
	require additional examinations/procedures and/or referral to a specialist, it	
	should be reported as a standard AE.	
Neurocognitive events	All neurocognitive events will be considered as AESI.	

10.5. Safety instructions related to investigational product 10.5.1 Local tolerability (local injection site reactions)

In case the Investigator or patient recognizes any signs of local intolerability, this should be treated and followed-up as per the Investigator's medical judgment. Specific electronic CRF screens are to be filled in. Local symptoms should be reported in the "local injection site reaction" section. If the injection site reaction progresses, both "local injection site reaction" and "general allergic reaction" of the form should be completed.

10.5.2 Allergic adverse events requiring consultation and local injection site reactions that are allergic and requiring consultation

Specific e-CRF screens are to be filled in to assess allergic reactions or allergic-like reactions requiring consultation with another physician that may occur. Transient injection site reactions, irritant in nature, that may occur but do not require intervention and are of dubious significance would not be considered to be allergic reactions. Adverse events that are obviously not of allergic origin (e.g., local injection site reactions related to mechanics of injection) should only be recorded on the Local Injection Site Reaction Complementary Form.

The IP should be immediately interrupted (temporarily discontinued) if there is a suspicion of an allergic event related to the IP. Re-initiation of the IP will be done under close and appropriate clinical/and or laboratory monitoring once the Investigator will have considered according to his/her best medical judgment that the responsibility of the IP in the occurrence of the concerned event was unlikely and if the selection criteria for the study are still met.

The Investigator should exercise medical judgment concerning the handling of all background/ concomitant medications potentially related to an allergic event.

10.5.3 Allergic adverse event with cutaneous involvement

Adverse events (AE) with cutaneous involvement which are obviously of allergic origin or injection site reactions which progress/expand/worsen should be evaluated by a dermatologist as soon as possible, and preferably within one week of the site first becoming aware of the event. The Investigator should evaluate the patient for possible etiologies (e.g., new medications) and extracutaneous symptoms and signs. An unscheduled assessment for hematology, chemistry, liver panel should be obtained. If possible, the site will take pictures of the skin lesions in order to provide the patient with them for the dermatologist's visit. If the photos are obtained, then copies should be kept as source documents which may later be collected and transmitted to Sanofi PV. The Investigator will provide a summary of the patient's case, reason for consultation, and information being requested to the consulting dermatologist.

A full consultation report should be sent by the dermatologist to the Investigator. The full report should contain, at a minimum, the following information; a detailed description of the rash (such as the morphology [lesion type], shape of individual lesions, arrangement of multiple lesions [e.g.,

scattered, grouped, linear], distribution, color, consistency, presence of pruritus or pain, and other clinical signs) and in case a skin biopsy (including histopathology and immunofluorescence) was done (if it was deemed necessary as per the dermatologist's or Investigator's medical judgment), the results of this investigation with, if applicable, a specific diagnosis of the AE. The Investigator will fax the full report and the corrected AE form if necessary, to the monitoring team representative within 24 hours and Sanofi PV.

10.5.4 Acute allergic injection reactions

Acute allergic injection reaction (which are considered under the category of general allergic reactions) is defined as any AE that occurs during or shortly after injection of the IP characterized by - but not limited to - hypotension, bronchoconstriction, urticaria, edema, angioedema, nausea, vomiting. Emergency equipment and medication for the treatment of these potential adverse effects (e.g., antihistamines, bronchodilators, IV saline, corticosteroids, acetaminophen, and epinephrine) must be available for immediate use for the injection at the inclusion visit.

Patients will be observed at the investigational site for at least 30 minutes following the injection that takes place at hospital. Patients should be treated symptomatically if any AEs are observed. Patients are to remain at the site until any acute injection reaction is assessed as stable, at the Investigator's discretion. General Allergic Reaction and/or Local Injection Site Reaction Complementary Form will have to be completed.

10.5.4. Neurocognitive side effects

In case of a suspected neurocognitive side effects (<0.2%), the study patients would be referred to a neurologist for further clinical evaluation prior to the next scheduled IMP administration.

10.6 Reporting of adverse events/ SUSAR/AESI

AE and SAE will be consistently documented.

The local Investigator will report all Serious Adverse Events (SAEs) regardless of the relationship to the investigated medicinal product and all Adverse Events of Special Interest (AESIs) (a) to the Sponsor/Coordinating Investigator within 24 hours of becoming aware of the event. If the event is fatal, it must be reported by the local Investigator to the responsible Ethics Committee within 7 days or according local regulations and requirements.

A SUSAR needs to be reported to the responsible Ethics Committee and to the health/ regulatory authorities (via Sponsor / Coordinating Investigator) within 7 days if the event is fatal, or else within 15 days (all other events) or according local regulations and requirements. The Sponsor / Coordinating Investigator must inform all Investigators participating in the clinical study of the occurrence of a SUSAR.

All SAEs will be followed until the event has resolved (with or without sequelae). All deaths, regardless of underlying cause and relationship to study drug, will be reported as SAEs up to the last visit of the patient.

This reporting requirement is applicable to SAEs/AESIs that occur during the designated study period. If the Investigator is notified of an SAE/AESI after the end of the study and the Investigator feels that this SAE is causally related to the study drug, the Investigator should report this event through the process described above in this paragraph.

Version 8, January 21, 2020

Confidential

All Serious Adverse Events (SAEs) regardless of the relationship to the investigated medicinal product and all Adverse Events of Special Interest (AESIs) must be transmitted to Sanofi PV within 1 business day of the Sponsor's awareness. The Sponsor/Coordinating Investigator must provide to Sanofi, upon request, results of any relevant complementary exams performed to obtain the final diagnosis of any SAE or AESI (e.g. hospital discharge summary, autopsy, consultation).

11. SAFETY AND FEASIBILITY OF INTRACORONARY IMAGING IN THE SETTING OF ACUTE MYOCARDIAL INFARCTION

At baseline (Day 1), study procedures for intracoronary imaging (IVUS, NIRS, OCT) are expected to increase the length of the cardiac catheterization by approximately 30-40 minutes. Potential, generally acknowledged risks of cardiac catheterization include a risk of death, myocardial infarction, or stroke of approximately 1 in 1000. However, the index cardiac catheterization and PCI will be performed only for clinical indications (acute myocardial infarction) and not for the purposes of the study. The incremental risks are only those associated with the intracoronary imaging procedures; importantly, IVUS is generally a very safe and routine clinical procedure. The study will require no additional inhospital time. The repeat cardiac catheterization at Week 52 is associated with similar risk as the initial procedure (approximately 1 in 1000 of life threatening complications or a small risk of coronary artery damage by IVUS less than 1%).

Our group has specifically tested the feasibility, procedural and long-term safety of intracoronary imaging with OCT and IVUS in patients with acute STEMI undergoing primary PCI in the setting of the IBIS-4 study.³⁵ Imaging of the non-infarct-related artery at baseline and follow-up was successful in 88.7% and 95.6%, respectively, of patients using OCT and in 90.5% and 93.3%, respectively, using IVUS. Peri-procedural complications occurred less than 2.0% of OCT (arrhythmia, resolved with electroconversion) and none during IVUS, and there were no differences throughout 2 years as compared with a control group of 485 STEMI patients undergoing primary PCI without additional imaging in terms of major adverse cardiac events (16.7% vs 13.3%, adjusted HR1.40; 95%CI 0.77-2.52; p=0.27). These data demonstrated that multi-modality three-vessel intracoronary imaging in STEMI patients undergoing primary PCI is feasible and can be performed safely without a significant impact on cardiovascular events at long-term follow-up.⁵⁷ Similar to IBIS-4, two catheters will be used (IVUS-NIRS combined catheter and OCT catheter). Consistently, we expect that performance of intracoronary imaging will be at least as safe in the present study that will also enroll relatively lower-risk patients with NSTEMI.

12. STATISTICAL CONSIDERATIONS

12.1 Pre-specified sample size calculation

12.1.1 Evidence of effect sizes on PAV. Previous serial IVUS studies assessing the effect of different statin doses on PAV by IVUS showed a dose-response relation between changes of PAV and doses of statin (and consequently, magnitude of LDL-C reduction). In the CAMELOT trial, a PAV increase of +1.3% was seen in placebo patients who received standard-of-care statin regimens.⁵⁸ Hong et al.⁵⁹ found that rosuvastatin 20mg resulted in -0.46% reduction of PAV at 11 months. Using a higher-dosed statin regimen, we recently reported a 43% reduction of LDL-C at 13 months with rosuvastatin

40mg and a PAV reduction of -0.90% at 13 months.³⁵ Consistently, a 53% LDL reduction and -0.98% PAV reduction at 24 months with rosuvastatin 40mg was reported in the ASTEROID trial,¹⁰ and a 44% LDL-C reduction and -1.23% PAV reduction was found in the SATURN trial at 24 months.¹¹ Of note, a sub-analysis of our data from the IBIS4 trial demonstrated that patients with more pronounced (above-median) LDL-C reduction had an average PAV reduction of -1.66 %, whereas in patients with less pronounced (below-median) LDL-C reduction the decrease of PAV was only -0.16%.³⁵ This finding indicates that differences in the magnitude of LDL-C reduction are associated with a difference of the order of $\pm 1.5\%$ in PAV change within a single cohort. Of note, the addition of ezetimibe to atorvastatin in the PRECISE-IVUS trial resulted in incremental LDL-C lowering and PAV reduction compared with treatment with atorvastatin alone, an effect that was most pronounced in patients with acute coronary syndromes (i.e., similar to patients in the present study) as compared with patients with stable coronary artery disease.⁶⁰

12.1.2 Rationale for expected effect size in each treatment arm. In summary, the observed range of PAV change over 1-2 years is in the range -1.2% to +1.3% in previous statin trials, with highest-dose statin regimens consistently associated with a PAV reduction of the order -0.90% to -1.23%. Along this line, the addition of alirocumab to maximally tolerated statin doses resulted in an incremental LDL-C reduction by 29.8% as compared to patients treated with maximal tolerated statin doses plus ezetimibe, with the proportion of patients reaching the LDL-C target of 70 mg/dl (1.8 mmol/L) being 77% vs. 45.6% and the proportion of patients reaching the extremely low LDL-C target of 50 mg/dl (1.3 mmol/L) being 60.3% vs. 14.2%, respectively.²⁷ Given the substantial incremental LDL-C reduction with alirocumab on top of maximally tolerated statin doses, we consider that a reduction in PAV beyond -1.23% is possible and we assume an expected PAV reduction of -1.8% in the PCSK9 inhibitor arm after 1 year. For the placebo arm of the proposed study that will receive rosuvastatin 20mg, the results by Hong et al⁵⁹ provide a reasonable benchmark to assume a moderate expected PAV reduction of -0.5%.

12.1.3 Sample size calculation. This is a superiority trial powered on the primary endpoint, change in PAV from baseline to 52 weeks (12 months). We assume a PAV change of -0.5% in the placebo arm and -1.8% in the alirocumab arm, with a common standard deviation of 3.4% (as a consensus from SATURN¹¹: 3.0%, IBIS4³⁵: 3.4%, ASTEROID¹⁰: 4.0%) and an intraclass correlation coefficient of *ICC*=0.40 (estimated from IBIS4 data). Given that *m*=1.8 vessels per patients are expected to be analyzed, this gives a *design effect* of *D*=1.4 [design effect computed as D = 1+ICC(m-1)]. If dropout was ignored, a total sample size of 176 patients would be necessary to reach a statistical power of 80% at a two sided alpha level of α =5%. Anticipating a dropout rate of 25% at the 12 month imaging follow-up, a total of n=220 patients should be recruited (110 per arm). See Appendix 1 for adjusted sample size and statistics

12.1.4 Pre-specified protocol amendment with revised sample sized calculation. The GLAGOV study is currently testing the effect of evolocumab on PAV regression by IVUS in a multi-center study including 968 patients. Study outcomes are expected to be presented in Q4, 2016. In case GLAGOV reports considerably lower PAV regression compared with our current assumptions (1.6% reduction or less), a protocol amendment of the present study will be submitted with a revised sample size calculation considering for the GLAGOV results. No amendment will be made in the present study if the GLAGOV findings exceed our present assumptions regarding PAV regression.

See Appendix 1 for adjusted sample size and statistics

12.2 Pre-specified statistical analysis of endpoints.

The primary analysis aims at comparing the active treatment (alirocumab) group with the placebo group in terms of the primary endpoint. The primary endpoint is defined at vessel level (matched ROI within vessels) and will therefore be analyzed with linear mixed models where the treatment arm represents the fixed effect and patient identifier is included as random intercept to account for the non-independence of endpoints measured on the same patient. This is a superiority trial and two-sided p-value will be reported. Only vessels with baseline and follow-up measurement available will be analyzed. The primary endpoint, change in PAV, is expected to be close to normally distributed, hence transformation would not be necessary. Superiority of the active treatment will be declared if the mean change in PAV is larger than the mean of the placebo arm and if the corresponding p-value is ≤ 0.05 . The secondary endpoints (macrophage AAE and LCBI_{total}) are expected to have a skew distribution;⁴⁹ if necessary, an adequate transformation will be used prior to deriving the change and estimating the p-values. Primary analyses will be based on the intention to treat principle (ITT). A sensitivity analysis for patients with missing data will be conducted and baseline characteristics will be compared with those of patients with complete data.

See Appendix 1 for adjusted sample size and statistics

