3.2. Number of patients

A total of 294 patients will be randomized in a 1:1 ratio to either alirocumab or placebo. Patients will be screened for eligibility based on anatomic criteria (number of arteries without significant obstructive atherosclerotic disease), estimated suitability for intracoronary imaging of 2 non-infarct-related coronary arteries, clinical and LDL-C level inclusion criteria as detailed in **section 4**. Justification of the sample size is described in: .

Please see Appendix 1 to Protocol for adjusted sample size

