Eligible patients will be considered enrolled once the consenting form has been signed and they will subsequently receive a unique Secutrial identifier, assigned by a web-based database system. The identifier will remain constant throughout the entire clinical study. Additionally, a blinded randomization identifier will be assigned when the patient is randomized. Randomization of enrolled patients will be performed only in patients with successful 2-vessel intracoronary imaging (or exceptionally also two regions of interest in the same vessel, e.g. in case of minimal caliber of one of the two non-infarct related vessels two ROI may be obtained in the larger non-infarct related vessel.), defined as successful imaging of the 2 imaging target vessels, at minimum by means of IVUS (modality used for the study's primary endpoint). Intracoronary imaging will be performed as deemed clinically feasible and safe by treating operators, aiming at successful imaging but without compromising patient safety according to physician's judgment. Imaging will be performed preferably immediately after PCI and latest within 24 hours after PCI. A screening log of all enrolled patients who undergo (successful or unsuccessful) intracoronary imaging will be maintained on the database A total of 220 enrolled patients will be randomized. Justification of the sample size calculation is described in Section 13.1.

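### Section 5.2 still randomises 220 patients where the rest of the protocol says 294, and the retained calculation behind 220 (Section 12.1.3) does not follow from its own inputs

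*Protocol*

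**What the plan says.** Two randomisation targets stand in the current protocol.

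- Section 5.2: "A total of 220 enrolled patients will be randomized". It cites Section 13.1 for the justification and does not mention Appendix 1.
- Section 3.2: "A total of 294 patients will be randomized in a 1:1 ratio to either alirocumab or placebo". The synopsis agrees (147 per arm), as does the milestone table in Section 13.7. Section 3.2 and the synopsis send the reader to Appendix 1 for the adjusted size.

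The derivation in Section 12.1.3 runs as follows.

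- Effect and spread: "We assume a PAV change of -0.5% in the placebo arm and -1.8% in the alirocumab arm", "with a common standard deviation of 3.4"%.
- Clustering: "an intraclass correlation coefficient of *ICC*=0.40 (estimated from IBIS4 data"). "Given that *m*=1.8 vessels per patients are expected to be analyzed", and "this gives a *design effect* of *D*=1.4 [design effect computed as D = 1+ICC(m-1")].
- Result: 176 patients before dropout, for 80% power at a two-sided 5% level.
- Dropout: "Anticipating a dropout rate of 25% at the 12 month imaging follow-up, a total of n=220 patients should be recruited (110 per arm").

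The section closes with a pointer to Appendix 1. Section 12.1.4 had planned in advance for a revised calculation if an external PCSK9-inhibitor imaging trial showed less regression than assumed.

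**The concern.** The number to randomise should be the same wherever the protocol states it, and a reader should be able to rebuild it from the assumptions given. Neither holds for 220. The section that tells sites how patients are enrolled and randomised gives a target 74 patients below the one in the synopsis and Section 3.2 (294 − 220 = 74), and its cross-reference leads to a section with no calculation. In the section that does hold the calculation, the design effect, the number before dropout and the dropout allowance each fail a direct check. At stake is whether the recruitment target and the stated power can be traced and agree throughout the document.

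**Working it through.** **Inputs, all from Section 12.1.3.** Difference 1.8 − 0.5 = 1.3 points; SD 3.4; ICC 0.40; m = 1.8 vessels per patient; power 80%; two-sided α = 5%; dropout 25%.

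**Step 1: design effect.** Formula as printed: D = 1 + ICC(m − 1).
- With m = 1.8: 1 + 0.40 × 0.8 = **1.32**.
- The stated 1.4 is 1 + 0.40 × 1, that is, m = 2. Rounding does not explain it, since 1.32 rounds to 1.3.

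**Step 2: patients before dropout.** Independent vessels per arm:
- Normal approximation: 2 × [3.4 × (1.960 + 0.842) / 1.3]² = 107.4, so 108.
- t-test: 108.3, so 109.

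Total patients = 2 × vessels per arm × D / m:

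| D | Normal (108) | t-test (109) |
|---|---|---|
| 1.32 | 216 × 1.32 / 1.8 = 158.4; 160 with equal whole arms | 218 × 1.32 / 1.8 = 159.9, so 160 |
| 1.4 | 216 × 1.4 / 1.8 = 168 | 218 × 1.4 / 1.8 = 169.6, so 170 |

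Neither row gives 176. To reach 176 with D = 1.4 would take m of about 1.71 (2 × 107.4 × 1.4 / 176) or a power of about 82%. Neither is stated.

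**Step 3: dropout.** The stated figure is reproduced exactly by 176 × (1 + 0.25) = **220**. To retain 176 after losing 25%, the number must be divided by the fraction retained:
- 176 / 0.75 = 234.7, so **235** (236 for equal arms).
- 220 retains 176 only if dropout is 1 − 176/220 = 20%.
- At 25% dropout, 220 × 0.75 = 165 remain.

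**Step 4: the whole chain redone** (t-test numbers).
- D = 1.32: 160 evaluable; 160 / 0.75 = 213.3, so **214** randomised.
- D = 1.4: 170 evaluable; 170 / 0.75 = 226.7, so **227** randomised.

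The stated 220 lies between the two. The 235 belongs only with 176 kept as it stands; it must not be paired with D = 1.32.

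**Step 5: power with 165 evaluable patients.** Effective vessels per arm = (165 / 2) × 1.8 / D.
- D = 1.4: 106.1 vessels, power 79% (t-test; 79.5% normal).
- D = 1.32: 112.5 vessels, power 81% (t-test; 81.8% normal).

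**The case against.** **The paragraph is superseded.** Section 12.1.3 ends by deferring to Appendix 1, and 294 is the target in the synopsis, Section 3.2 and Section 13.7. On this view Section 5.2 holds one stale sentence, and errors in a retained calculation no longer set recruitment. That stands as far as consequence goes. It does not remove the contradiction, because Section 5.2 carries no pointer to Appendix 1 and cites the wrong section. Nor does it make the arithmetic in Section 12.1.3 right, because nothing but the closing pointer marks that text as historical.

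**A design effect near 1.4 can be defended.** Suppose m = 1.8 means that 80% of patients have two analysed vessels and 20% have one (an assumption; the protocol does not say so). The design effect for unequal clusters uses E[m²]/E[m] = (0.8 × 4 + 0.2 × 1) / 1.8 = 1.889, so D = 1 + 0.40 × 0.889 = 1.356. Then 218 × 1.356 / 1.8 = 164.2 evaluable, and 164.2 / 0.75 = 219 randomised, very close to 220. This supports the size of the old target. It is not the printed formula, however, and it does not produce 176.

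**Stronger readings to resist.**
- A reader might infer that the original design was underpowered because 165 falls short of 176. But the 176 is itself not reproducible and too high for the stated inputs; 165 gives about 79 to 81% power.
- A reader might also infer that 294 is unsupported, or that the dropout slip was carried into it. Appendix 1 is not in the text at hand, so the basis of 294 cannot be judged either way.
- Nor can a power be attached to 294 from the Section 12.1.3 inputs, because Section 12.1.4 foresees that a revision would rest on a different effect.

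**Conclusion.** The point holds as a matter of consistency and traceability. Section 5.2 contradicts three other places on the number to randomise, by 74 patients, and cites a section that contains no sample size calculation. In Section 12.1.3 the design effect should be 1.32 under the printed formula, 176 is not reproduced (about 160 or 170), and 220 allows for 20% dropout rather than the stated 25%.

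The practical effect on the original design is small because the errors pull in opposite directions: the redone chain asks for about 214 to 227 randomised against the stated 220. No shortfall in power is shown, and nothing here bears on whether 294 is adequate. These figures assume the protocol's own difference, SD, ICC and m, a two-sample comparison of vessel-level means, and 25% loss at follow-up imaging.

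The contradiction over 220 and 294 is the part that most needs correcting. The arithmetic alone is minor.

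**What to change.** 1. Section 5.2: change 220 to 294, and replace the reference to Section 13.1 by one to Section 12.1 and Appendix 1.
2. Section 12.1.3: reconcile the design effect with m and the formula. Either state 1.32, or justify m = 2, or print the formula that was used (for example, one for unequal numbers of vessels per patient).
3. Restate the evaluable number that follows (about 160 at D = 1.32, 170 at D = 1.4), and inflate it by 1/(1 − 0.25), giving about 214 or 227.
4. Label the paragraph as the original calculation, superseded by Appendix 1, so that its result is not read as the current target.

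This is a text correction. It leaves the 294 target, the treatment and the analysis as they are.
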